## 8. Statistical Analysis

The primary analysis will be performed using an ‘intention to treat’ analysis. Using this approach, patients will be included in the analysis according to the group to which they were randomized regardless of cross-over or compliance. Baseline characteristics of patients in the two treatment arms will be assessed using frequency distributions and univariate descriptive statistics including measures of central tendency and dispersion. As a complementary approach,

we will also conduct a treatment received as ‘per protocol’ analysis of the primary outcome measures. Baseline characteristics in the two treatment arms will be compared using univariate descriptive statistics.

The primary analysis of the composite outcome of two-year cancer recurrence and mortality will be conducted using an unadjusted chi-square test comparing the proportion of events in each of the two treatment groups. This will be translated into a relative risk (RR), relative risk reduction (RRR), absolute relative risk (ARR), and number needed to treat (NNT). In addition, a logistic regression procedure will be employed to adjust exacerbation proportions using covariates that are either clinically important prognostic risk factors or unbalanced at baseline.

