**Protocol Amendment: March 6th 2013**

**Protocol Amendment: March 19th 2014**

**Protocol Amendment: December 8th 2014**

## 1. Background and Rationale

Lung cancer accounts for the greatest incidence of cancer mortality worldwide; more than colon, gastric, prostate and breast cancer combined, in men and women respectively [1]. According to a 2002 report by the International Agency for Research on Cancer, lung cancer was responsible for 1.18 million deaths yearly [2]. Non-small-cell lung cancers (NSCLC) comprises the vast majority of cases accounting for 80% of lung cancer diagnoses [3]. Surgical resection followed by adjuvant platinum-based chemotherapy remains the standard of care, offering the best chance for long-term care in patients with resectable disease who can tolerate surgery [4, 5]. Despite optimal therapy, however, loco-regional or systemic recurrence occurs in an unacceptably high proportion of patients, leading to mortality in the vast majority of those patients [6].

A recently validated prognostic index designed for NSCLC gives some measure of expected mortality in patients with this disease [3]. The patient's index is scored based on performance status, age, sex, histological type, and TNM staging. Using this index system and dividing the risk strata into five categories, the rates for 2-year mortality in each respective quintile are: 1st: 39%; 2nd: 72%; 3rd: 81%; 4th: 93%; and 5th: 96% [3]. Using the more standard International System for Staging Lung Cancer, 2-year survival based on initial diagnosis of clinical disease stage is: IA: 82%; IB: 59%; IIA: 57%; IIB: 43%; IIIA: 27%; IIIB: 15%; and IV: 10% [7].

[figure not shown]

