#### **6.4 Interventions**

Patients who appear to meet eligibility criteria will be approached and asked to consent to the trial by the research coordinator. After eligibility criteria have been confirmed by the investigator or medically qualified delegate patients will be randomized using a centralized system at The Ottawa Hospital to either active melatonin group or placebo. Randomization will be stratified according to cancer staging (I/II vs. III/IV). Allocation bias will be prevented by using a randomization table with variable blocks of 4 and 6. Only the Pharmacy Research Technician at the Ottawa Hospital can see the randomization table and treatment assignments.

Patients, physicians, and the research coordinator will be kept strictly blinded as to individual group allocation and treatment. The intervention, active or placebo, will be given to participants in opaque bottles with the patient study code clearly written on the corresponding container. The clinical trial pharmacist at the coordinating site will be responsible for the coding and container labeling of all containers. Instructions for taking the intervention will be identical for both control and melatonin groups. The research coordinator will be responsible for the dispensing of the pills (both active and placebo).

Melatonin or placebo will be provided to patients either on the day of discharge or up to 60 days post-operative from the hospital. In the phase II substudy, participants will only be given the intervention four weeks following surgery. This wait period is to reduce the confounding effect of the surgery on the surrogate measures we are testing. Patients will be responsible for taking their doses and will be required to report any missed doses to the research coordinator. To ensure optimal compliance, the research coordinator will telephone each patient once a week for two weeks at the beginning of the trial. Telephone calls will then be made as needed until the completion of one year while the patient is on the study drug.

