## **6.5 Outcome Measures**

The primary outcome is a composite outcome including either cancer recurrence and/or mortality within two years following the commencement of the intervention. Recurrence will be determined by clinical examination by the patient's thoracic surgeon in addition to radiological evidence of loco-regional or systemic recurrence of lung cancer. While contrast enhanced chest CT scan at one and two years post resection is the preferred radiological assessment, the standard of care radiological assessments for each site is acceptable. For study purposes, only chest CT is requested at 1 and 2 years, but results of head and abdominal CTs will be recorded if applicable. As per standard of care, lateral and P/A chest radiographs will be assessed at 3 weeks and at 3, 6, 9, 12, 18 and 24 months following hospital discharge.

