## NSCLC Adjuvant melatonin RCT

[figure not shown]
we essentially have 100% power to detect this difference i.e. this difference will be incredibly unlikely to be missed due to chance.

*Figure 2: For group rates of 20 % and 5 %, power versus sample size per group for different null rate differences.*

In the third and final graph (Figure 3) if we see an event rate of 20% which is also possible in our population and there is a drop of only 5% we are actually powered to nearly 90% with a population of 640.

*Figure 3: For group rates of 20 % and 15 %, power versus sample size per group for different null rate differences.*

For the phase II sub-study, we are interested in exploring potential mechanisms through which melatonin may be exerting activity. An exploratory pilot analysis of 80 subjects will provide information on what is occurring physiologically and is powered to see a 30% significant shift in NK cell functional activity. In addition, with 40 patients in each group, the expected number with recurrence or mortality is expected to be approximately 16 subjects, allowing for comparison of the NK cell function and biologic markers amongst this subgroup, compared to those without recurrence for both the melatonin and the control groups.

Although sample size calculation represent only rough estimates of the true sample required [79], confidence intervals around the primary endpoint will provide strong inferences into how well powered the trial is. It should be noted that our proposed sample is much larger than any of the previously conducted melatonin/cancer trials for which a statistically significant reduction in mortality was found after only one year. Given the sample size we will accrue, we confidently anticipate that the trial is well powered to address the primary objective without undue use of time and resources. The addition of the mechanistic substudy and trial extension will greatly extend the impact of the trial and potential for strong results to lead to policy shifts and a change in pattern of clinical practice leading to better patient care.

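### The primary chi-square ignores the stage stratum used at randomisation: valid but conservative, with a small, avoidable loss of precision; the supporting logistic model also lets observed imbalance choose covariates

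*Combined protocol and SAP*

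**What the plan says.** - Section 6.4 (Interventions): "Randomization will be stratified according to cancer staging (I/II vs. III/IV"). The same paragraph adds: "Allocation bias will be prevented by using a randomization table with variable blocks of 4 and 6".
- Section 6.5 (Outcome Measures): "The primary outcome is a composite outcome including either cancer recurrence and/or mortality within two years following the commencement of the intervention". The endpoint is therefore binary.
- Section 8 (Statistical Analysis): the primary analysis "will be conducted using an unadjusted chi-square test comparing the proportion of events in each of the two treatment groups", reported as relative and absolute risk measures and NNT. No stage term appears. A further logistic regression may adjust for "covariates that are either clinically important prognostic risk factors or unbalanced at baseline"; no covariate is named.
- Section 1 (Background and Rationale) gives two-year survival by clinical stage, in percent, as "IA: 82%; IB: 59%; IIA: 57%; IIB: 43%; IIIA: 27%; IIIB: 15%; and IV: 10". It also cites a prognostic index whose "index is scored based on performance status, age, sex, histological type, and TNM staging".
- Section 7.0 (Sample Size Determination) plans for 640 patients, 320 per arm. One of its cases is: "if we see an event rate of 20% which is also possible in our population and there is a drop of only 5" percentage points.

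**The concern.** Blocked randomisation within stage makes the arms nearly equal on stage, so the true variance of the difference in proportions contains almost no between-stage component. The ordinary chi-square variance still includes that component. The standard error is then overstated, the true size falls below the nominal level, and an unstratified interval is wider than the design warrants. The benefit of stratifying is not collected in the primary analysis.

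The logistic model raises a separate, smaller point. Stage is not guaranteed to be in it, because the prognostic factors are not listed. Its second entry route selects covariates from the observed baseline data. That does not touch the primary p-value, but it leaves the adjusted estimate open to choice once the data are seen.

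**Working it through.** **The plan's own figure first.** The documents state neither alpha nor sidedness; two-sided 5% is assumed. For 320 per arm, power = Φ((|p1 − p2| − 1.96·SE0)/SE1), where SE0 uses the pooled rate and SE1 the separate rates.

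- 5% against 11%: 0.800. 5% against 12%: 0.890. These agree with the stated 80 to 90%.
- 20% against 15%: SE0 = √(2 × 0.175 × 0.825/320) = 0.03004 and SE1 = √((0.16 + 0.1275)/320) = 0.02997, so power = Φ((0.05 − 0.05888)/0.02997) = Φ(−0.296) = 0.384. Section 7.0 claims nearly 90% here. That is a separate sample-size problem, which stratifying does not repair.

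**Strength of stage.** Odds of death at two years, from the Section 1 survival figures:

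- IIIA: 0.73/0.27 = 2.704
- IIB: 0.57/0.43 = 1.326, so the odds ratio of IIIA to IIB is 2.0 (smallest contrast)
- IB: 0.41/0.59 = 0.695, so 3.9 (middle)
- IA: 0.18/0.82 = 0.220, so 12.3 (extreme; it treats every stage I/II patient as IA)

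**Assumptions.** Overall control rate 20% (Section 7.0); stage III/IV share w of 5, 10, 20 or 30%; these odds ratios carried over to the composite endpoint. The control rates p1 (I/II) and p2 (III/IV) solve (1 − w)p1 + w·p2 = 0.20 with the chosen odds ratio.

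**Formulas under no treatment effect.**

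- Within-stage share of variance: r = [(1 − w)p1(1 − p1) + w·p2(1 − p2)]/(0.20 × 0.80)
- True size of the unadjusted test: 2Φ(−1.96/√r)
- Excess interval width: 1/√r − 1
- Equivalent extra patients from stratifying: 1/r − 1

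**One case in full: w = 20%, middle contrast.** p1 = 0.149 and p2 = 0.405. The numerator is 0.8 × 0.149 × 0.851 + 0.2 × 0.405 × 0.595 = 0.1014 + 0.0482 = 0.1496. Then r = 0.1496/0.16 = 0.935 (0.934 before rounding the rates), 1/√r − 1 = 3.4%, 1/r − 1 = 7.0%, and size = 2Φ(−2.03) = 0.043. Simulation gave 0.042.

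**All twelve cases.** Size and power come from 200,000 simulated trials each: 320 per arm, equal allocation within stage, no continuity correction. For power, a common treatment odds ratio takes the treated arm to 15% overall.

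| III/IV share | Contrast | p1, p2 | r | Interval wider | Extra patients | Chi-square size | Power %, chi-square → CMH |
|---|---|---|---|---|---|---|---|
| 5% | smallest | .193, .328 | .995 | 0.3% | 0.5% | .050 | 38.4 → 38.7 |
| 5% | middle | .186, .470 | .976 | 1.2% | 2.5% | .048 | 38.1 → 39.1 |
| 5% | extreme | .173, .720 | .911 | 4.8% | 9.8% | .040 | 37.8 → 41.7 |
| 10% | smallest | .187, .319 | .990 | 0.5% | 1.0% | .049 | 38.2 → 38.7 |
| 10% | middle | .172, .448 | .957 | 2.2% | 4.5% | .045 | 38.1 → 39.8 |
| 10% | extreme | .147, .679 | .840 | 9.1% | 19.0% | .032 | 37.2 → 44.4 |
| 20% | smallest | .175, .301 | .984 | 0.8% | 1.6% | .048 | 38.3 → 38.9 |
| 20% | middle | .149, .405 | .934 | 3.4% | 7.0% | .042 | 38.0 → 40.5 |
| 20% | extreme | .103, .587 | .766 | 14.2% | 30.5% | .026 | 36.6 → 47.0 |
| 30% | smallest | .164, .285 | .981 | 1.0% | 2.0% | .048 | 38.2 → 38.9 |
| 30% | middle | .129, .366 | .927 | 3.9% | 7.9% | .042 | 37.9 → 40.7 |
| 30% | extreme | .074, .495 | .767 | 14.2% | 30.3% | .025 | 36.9 → 46.5 |

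The CMH size was 0.049 to 0.051 throughout.

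**Cross-check with the actual blocks of 4 and 6.** With 20% in III/IV and control rates of 15% and 40%, the size was 0.043 (chi-square) against 0.050 (CMH), and power 0.382 against 0.403. With no stage effect, size was 0.051 and power 0.384 for both tests.

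**The plan's other cases, same contrasts and shares.** Gain in power from stratifying, in percentage points:

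| Case | Smallest | Middle | Extreme |
|---|---|---|---|
| 5% v 11% | 0.2–0.4 | 0.5–1.0 | 2.5–3.4 |
| 5% v 12% | 0.1–0.3 | 0.4–0.6 | 1.6–2.1 |
| 20% v 5% | none | none | none |

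**The case against.** An unadjusted chi-square after stratified randomisation is prespecified, simple and valid, so preferring CMH is a matter of efficiency. That is right, and it sets the weight of this point.

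The 20% against 15% case is the planning case where stratifying gains most. At the lead case, 5% against 11% or 12%, the gain outside the extreme contrast is at most about one point. This also stands.

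The stage contrasts are borrowed. Section 1 reports death by clinical stage at diagnosis, whereas the trial enrols patients scheduled for resection, excludes those whose cancer cannot all be resected (Section 5.2), and counts recurrence as well as death. The odds ratio of 2.0 is not a floor: at 1.5 the gain at 20% against 15% is at most about 0.2 points. So the size is uncertain and the extreme rows should carry little weight. The direction does not change.

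The logistic model may well include stage as a clinically important factor. But it is additional, names nothing, and yields a conditional odds ratio; it leaves the primary test and its risk measures unstratified.

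Section 8 gives no interval method, so the statement about width assumes an unstratified interval to match the test.

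A long covariate list could strain the logistic model. At 5% against 11%, 16 + 35.2, or about 51, events are expected. That is a reason to keep the list short and fixed.

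**Conclusion.** The concern holds, as a point of efficiency and prespecification rather than validity. The primary test ignores the randomisation stratum. Its size stays at or below 5% apart from simulation error, and it loses some precision whenever stage is prognostic. Under the assumptions above, small and middle contrasts give a true size of 4.2 to 5.0%, an interval 0.3 to 3.9% too wide, the equivalent of 0.5 to 7.9% more patients, and about 0.3 to 2.8 points of power at 20% against 15%. The extreme contrast gives a size of 2.5 to 4.0%, an interval about 5 to 14% too wide and about 4 to 10 points. The likely gain is modest, and it is about zero if stage is weakly prognostic in resected patients. CMH was not less powerful in any case examined.

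The data-driven covariate rule does not affect the primary p-value, but it leaves the adjusted estimate open to choice.

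**What to change.** Replace the primary-analysis sentence in Section 8 with wording such as:

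> Two-year recurrence or death will be analysed by a Cochran-Mantel-Haenszel test stratified by randomisation stratum (stage I/II or III/IV). The stage-stratified risk difference and the Mantel-Haenszel relative risk will be given with 95% confidence intervals. An unstratified chi-square test will be a sensitivity analysis.

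Derive the RRR and NNT from these stratified estimates.

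For the logistic model, remove the clause that admits covariates because of baseline imbalance and fix the list in advance: the stage stratum always, plus those of performance status, age, sex and histological type that are collected. Settle that list before the data are unblinded and keep it short in view of the expected number of events. The sentence should also name the trial's outcome; it now speaks of adjusting exacerbation proportions, which this trial does not measure.

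The cost is wording only. The stratum is already recorded for randomisation, and no patient, visit or data item changes. The primary test becomes slightly less simple.

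### The supportive adjusted analysis lists no covariates and admits them for chance baseline imbalance with no threshold, so the model can be chosen after the arms are compared

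*Combined protocol and SAP*

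**What the plan says.** Section 6.5 (Outcome Measures) defines the endpoint: "The primary outcome is a composite outcome including either cancer recurrence and/or mortality within two years following the commencement of the intervention". Section 8 says its primary analysis will be "conducted using an unadjusted chi-square test comparing the proportion of events in each of the two treatment groups", with the result expressed as a relative risk, a relative risk reduction, a quantity labelled absolute relative risk, and an NNT.

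A second analysis is added to that one: a "logistic regression procedure will be employed to adjust exacerbation proportions using covariates that are either clinically important prognostic risk factors or unbalanced at baseline". The covariate rule therefore has two routes. The first, prognostic importance, names no factor. The second, imbalance, has no cut-off. The only help with the second is that "Baseline characteristics in the two treatment arms will be compared using univariate descriptive statistics", which sets no criterion.

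Two other places bear on the choice. Section 1 cites a validated prognostic index for this disease whose "index is scored based on performance status, age, sex, histological type, and TNM staging". Section 6.4 (Interventions) stratifies randomisation by stage, I/II against III/IV. Neither the index factors nor the stratum is carried into Section 8.

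**The concern.** A covariate earns its place in an adjusted analysis by predicting the outcome. Observed imbalance between randomised arms is chance and says nothing about whether the variable predicts recurrence or death. A rule based on imbalance can be applied only once the arms have been compared, and without a threshold two analysts could follow it honestly and fit different models. The prognostic route is sound in principle, but with no list it is open in the same way.

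At stake is the credibility of the adjusted estimate, which will be read beside the primary result. As the plan stands, a reader could not tell whether the reported model was the planned one or the most favourable of several.

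**Working it through.** The documents attach no figure to the adjusted analysis, so there is none to reproduce. The check asks three things. All simulations use 320 per arm (Section 7); the covariate numbers, strengths, cut-offs and treatment effects are assumptions.

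**1. How often would the imbalance route be triggered by chance?** For k independent baseline variables and a cut-off a, the chance that at least one is flagged is 1 - (1 - a)^k. With k = 10:
- a = 0.05: 1 - 0.95^10 = 40%.
- a = 0.10: 1 - 0.90^10 = 65%.

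For k = 5 and k = 20 the values are 23% and 64% at 0.05, and 41% and 88% at 0.10. The plan describes baseline without tests, so these p-value cut-offs only illustrate what an unstated threshold could mean.

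**2. What does the rule do if both routes are applied together?** Set-up: 10 baseline variables, four of them prognostic (OR 1.65 per SD), flag at p < 0.10, 4,000 runs.

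| Model | Power | Type I error |
|---|---|---|
| Prognostic set, fixed | 75.9% | 5.1% |
| Prognostic or flagged (rule as written) | 75.7% | 5.3% |

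At a lower event rate, power was 56.1% for both. A separate simulation at about 40% events gave power of 79.0% for the rule as written against 79.4% for the fixed set, and type I error of 5.4% against 5.3%. With 4,000 runs, the simulation error on a 5% rate is √(0.05 × 0.95 / 4,000) = 0.34 percentage points, so the type I differences are within noise. Only comparisons within a pair carry meaning, because the treatment effect is assumed.

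**3. What does freedom to choose do?** Set-up: about 21% control events, 10 baseline variables, three prognostic (log-odds 0.6 per SD), flag at p < 0.10, 20,000 null runs. Three models could each be defended under the wording: the prognostic set, the imbalance set, or both.
- Prognostic set fixed in advance: type I error 5.0%.
- Imbalance set alone: 4.4%.
- Most favourable of the three: 6.2%.

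The simulation error is √(0.05 × 0.95 / 20,000) = 0.15 points, so the rise of 6.2 - 5.0 = 1.2 points is real under these assumptions. Further simulation gave 6.3-6.5% for the best of three.

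**The case against.** The strongest reply is that this is a secondary analysis, that its first-named route is accepted practice, and that adding a few chance-imbalanced covariates to a prognostic set does no measurable harm. All of that stands; step 2 confirms the last part. Imbalance could also be judged before outcomes are seen, but the plan does not say that it will be.

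A reader might infer four stronger things that the documents do not support.

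- *That the trial's main result is compromised.* The chi-square test is primary and uses no covariates, so its error rate is unaffected.
- *That the rule forfeits the precision adjustment can bring.* That would be true of a rule using imbalance alone: in the step 3 set-up with a treatment OR of 0.6 (8,000 runs), power was 58.5%, against 63.8% for the fixed prognostic set and 57.8% unadjusted. The plan's rule also admits prognostic factors.
- *That an adjusted odds ratio will be set beside the relative risk and look like a larger effect.* Section 8 mentions no odds ratio; it speaks of adjusting proportions, which can be read as adjusted risks. If the scale is discussed, the range matters. At Section 7's 20% v 15%, RR 0.75 corresponds to OR (0.15/0.85)/(0.20/0.80) = 0.71. At an assumed 40% v 30%, RR 0.75 corresponds to OR (0.30/0.70)/(0.40/0.60) = 0.64.
- *That the wrong outcome will be modelled.* Exacerbation is not an outcome in Section 6.5, but the same paragraph of Section 8 names the composite. This is a drafting slip, as is the label absolute relative risk.

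**Conclusion.** The concern holds as a weakness in a supportive analysis. The covariates are unlisted, one of the two routes into the model rests on chance imbalance with no threshold, and the choice can be made after the arms are compared. The size is modest: about 6.2-6.5% type I error instead of 5.0% if the most favourable of three admissible models is reported, and almost no change in power or type I error if the prognostic factors are always included and both routes are applied together. These values rest on assumed independent covariates, assumed strengths and a p < 0.10 flag. They do not count the further freedom in choosing the prognostic list or the cut-off, which was not quantified. The change is worth making because it is cheap and makes the adjusted result verifiable as planned.

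**What to change.** Keep the chi-square test as the primary analysis and replace the logistic regression sentence in Section 8 with:

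> In addition, the composite of recurrence or death within two years will be analysed by logistic regression adjusting for stage (I/II v III/IV, the randomisation stratum) and a list of prognostic factors fixed before unblinding (age, sex, histology, and performance status if recorded at baseline, from the index cited in Section 1), whatever the baseline balance. Adjusted risks will be standardised to give an adjusted RR, absolute risk reduction and NNT with 95% CIs.

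This removes the imbalance clause and the reference to exacerbation. As a further editorial correction, change absolute relative risk to absolute risk reduction in the sentence on the unadjusted result.

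The cost is one paragraph of the analysis plan and a check that the listed items are on the case report form or in the chart. Performance status needs that check most, because the data-collection text in Section 6.6 does not mention it. No visit, procedure or sample size changes.
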